7.6.3. Missing Dates

If a start or stop date for an adverse event or a concomitant medication use is completely missing, it will not be imputed. If it is partially missing, imputed dates in accordance with Table 5 will be used to derive the duration of the adverse event or the duration of the medication use. Missing years will not be estimated under any conditions. Missing dates of medical history will not be imputed.

Table 5: Imputation Rules for Partial Adverse Event or Concomitant Medication Start and Stop Dates

	Missing	Imputation	Exception
Start Date	Day	01	Default to Study Day 0 (day of first injection procedure) if an event starts in the same year and month as Study Day 0
	Day/Month	01JAN	Default to Study Day 0 if an event starts in the same year as Day 0
Start Date			If the start date is completely missing and stop date is either after the date of the first dose of study drug or completely missing, then the start date will be estimated to be equal to the date of the first dose of study drug. Otherwise, the start date will be estimated to be the first day of the same year as the stop date.
Stop Date	month stop		Default to the End of Study Date if the imputed event stop date is after the End of Study Date or before start
	Day/Month	31DEC	day of the event

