### **6.7.2. Medications and Procedures That May Interfere with Assessment of Pain**

Participants may participate in the study if they are willing to discontinue use of the following therapies 7 days prior to starting the 7-Day BPI-DPN eDiary. Participants must refrain from use of these therapies for the duration of the study:

- skeletal muscle relaxants
- opioids
- benzodiazepines (except for stable bedtime dose)
- injectable steroids
- capsaicin applied to the lower legs or feet
- local anesthetic creams and patches applied to the lower legs or feet (except local/topical anesthetic cream applied immediately prior to study drug injections)
- ISDN spray applied to the lower legs or feet
- transcutaneous electrical nerve stimulation (TENS), acupuncture

A list of prohibited medications and procedures in this category can be found in Section 10.4.

If not using a stable dose of duloxetine (Cymbalta), any antidepressants (e.g., amitriptyline and venlafaxine), or any other antiepileptics (e.g., valproic acid, carbamazepine, and vigabatrin) during Screening, Participants must agree to not start these drugs during the study. Potential Participants on these medications on the day of informed consent must maintain a stable dose during the study. Participants may not use pregabalin (Lyrica) or gabapentin (Neurontin) at any time during the study.

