8.3.1. Prior and Concomitant Medications

Prior medications are those medications taken within 30 days of the first injection of study drug. Concomitant medications are those medications taken after the initial dose of study drug. A medication with a missing start date and a stop date that is either missing or on or after the treatment start date will be considered as concomitant. All prior and concomitant medications will be assigned WHO drug names using the WHO Drug Dictionary (March 2018 version or later). Prior and concomitant medications will be summarized separately for each treatment group by preferred names. These summaries will present the number and percentage of participants using each medication.

[figure not shown]

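### SAP Table 5 moves some partial start dates to Day 0 without checking the stop date, so a record that ended before Day 0 gets a negative or a full-study duration

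*SAP*

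**What the plan says.** SAP 7.6.3 covers missing start and stop dates of adverse events and concomitant medication. The stated purpose of the imputed dates is to compute how long the event or the medication lasted. Table 5 gives these rules:

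- **Start date, day missing:** first of the month, with the exception "Default to Study Day 0 (day of first injection procedure) if an event starts in the same year and month as Study Day 0".
- **Start date, day and month missing:** 1 January, with the exception "Default to Study Day 0 if an event starts in the same year as Day 0".
- **Stop date, partly missing:** a default date, with the exception "Default to the End of Study Date if the imputed event stop date is after the End of Study Date or before start".
- **Start date completely missing:** when the record has no stop date, or one later than first dose, the rule reads "then the start date will be estimated to be equal to the date of the first dose of study drug". In all other cases it becomes 1 January of the stop year.

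The text above the table says: "If a start or stop date for an adverse event or a concomitant medication use is completely missing, it will not be imputed". It adds that a missing year is never estimated.

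SAP 8.3.1 and 8.5.3 have their own rule for a record with no start date. It counts as concomitant, or as a TEAE, if its stop date is missing or falls on or after the start of treatment.

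**The concern.** The two partial-start exceptions compare the known part of the start date with Day 0 and nothing else. If the recorded stop date shows that the drug or event was over before Day 0, the start is still moved to Day 0. The stop-date exception then does one of two things. A complete stop date is not imputed, so the exception does not apply and the record ends before it begins. A partial stop date is imputed, is found to precede the start, and is pushed to End of Study.

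Records that end before Day 0 are expected in this trial. Protocol 6.7.2 admits people who are "willing to discontinue use of the following therapies 7 days prior to starting the 7-Day BPI-DPN eDiary", and Schedule of Activities footnotes 18-19 collect start and stop dates of drugs taken from 30 days before consent. What is at stake is the correctness of derived durations and of listings that show the derived dates. The conflict between the text and the last start-date row also means that two programmers could follow the same section and obtain different dates.

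**Working it through.** The plan gives no figure to reproduce, so the check applies the rules as written to example records.

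**Inputs**
- Start and stop rules: SAP 7.6.3, Table 5. Complete dates are left as recorded.
- Stop date with missing day: month end. This is an assumption, because the cell is not fully legible in the available copy. The text of the exception is legible.
- Day 0 = 15 May 2021, chosen for illustration. End of Study = Day 180 = 15 May + 180 days = 11 November 2021.
- Duration = stop - start + 1.

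| Record | Start as recorded | Stop as recorded | Derived start | Derived stop | Duration (days) |
|---|---|---|---|---|---|
| A | 2021 | 10 Apr 2021 | 15 May 2021 | 10 Apr 2021 | -35 + 1 = -34 |
| B | 2021 | Mar 2021 | 15 May 2021 | 31 Mar, reset to 11 Nov 2021 | 180 + 1 = 181 |
| C | May 2021 | 6 May 2021 | 15 May 2021 | 6 May 2021 | -9 + 1 = -8 |
| D | Apr 2021 | 28 Apr 2021 | 1 Apr 2021 | 28 Apr 2021 | 27 + 1 = 28 |
| E | 2020 | 10 Apr 2021 | 1 Jan 2020 | 10 Apr 2021 | 366 + 100 = 466 |
| F | May 2021 | May 2021 | 15 May 2021 | 31 May 2021 | 16 + 1 = 17 |

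Records A to C ended before Day 0 and are derived wrongly. For a complete stop date g days before Day 0, the derived duration is always 1 - g (A: g = 35; C: g = 9). For a partial stop date that falls wholly before Day 0, it is always 181 with End of Study at Day 180. A and C do not depend on the month-end assumption.

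Records D to F mark the limits. In D the known month is not the Day 0 month, and in E the year is not the Day 0 year, so neither start is moved to Day 0. In F the stop is not known to precede Day 0, so no error is shown.

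**Text against table.** Take a record with no start date and stop 10 August 2021. Under the text of 7.6.3 the start stays missing and there is no duration. Under Table 5 the start becomes 15 May 2021 and the duration is 87 + 1 = 88 days. Both cannot be followed.

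**The case against.** **Scope.** The table is titled for adverse events and concomitant medication, and 8.3.1 says: "Concomitant medications are those medications taken after the initial dose of study drug". A drug stopped in Screening is therefore a prior medication and, on one reading, never reaches Table 5. For adverse events, 8.5.3 says that only those after the first injection are collected, which makes a Day 0 default sensible. This has weight but does not settle the matter. The last start-date row has a branch for stop dates that are not after first dose, so the table itself foresees such records. Section 7.6.3 does not say that records are classified before dates are imputed. The protocol (8.5.1 and Schedule of Activities footnote 28) also records adverse events from consent onward.

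**Use.** The imputed dates are stated to serve durations only, while 8.3.1 and 8.5.3 plan numbers and percentages of participants and numbers of events. No duration table appears. This stands and limits the effect.

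**Detection.** Routine checks would catch negative durations. That is true of A and C. It is not true of B, where 181 days looks like ordinary use throughout the study.

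**Frequency.** The protocol asks for start and stop dates for every medication, and drugs stopped in Screening are stopped while the site is in contact with the participant. Partial dates may be few. The documents do not say.

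**Stronger readings.** A reader might infer that every partial start date in the Day 0 year is moved; record D shows otherwise. A reader might also infer that a completed washout would count as prohibited use up to the Day 180 endpoint and disturb the per-protocol set or the deviation review. The documents do not support this. The per-protocol criteria in SAP 6.4 are eligibility, all injections received and a Day 180 visit with its diary, plus any that the Clinical Data Review Committee adds. Protocol 10.1.6.6 tracks deviations through the data capture system. Neither is tied to Table 5 dates.

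**Conclusion.** The rule is wrong as written. A record that ended before Day 0 gets a negative duration if its stop date is complete, or 181 days if its stop date is partial. This applies when the start has a missing day in the Day 0 month, or a missing day and month in the Day 0 year. Separately, 7.6.3 and its own table disagree on completely missing start dates.

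The effect per record is exact, given End of Study at Day 180 and, for the 181-day case only, month-end imputation. The number of records affected cannot be estimated from the documents. The direct harm is to derived medication and adverse event durations and to listings. Prior, concomitant or TEAE counts would change only if the imputed dates were also used for classification, which 7.6.3 does not state. No effect is shown on the ITT primary analysis, which rests on diary scores, or on per-protocol or deviation review. This is a small, definite error that is worth correcting before database lock.

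**What to change.** Amend SAP 7.6.3 and Table 5 as follows.

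1. In both partial-start rows, apply the Day 0 default only if the stop date is on or after Day 0, or is missing or ongoing. For a partial stop date, test its latest possible value. Otherwise keep the first of the month or 1 January.
2. Limit the End of Study default to imputed stop dates that fall after End of Study. Send a query for any stop date that still precedes its start.
3. Delete the row for completely missing start dates. The text of 7.6.3 then governs dates, and the rules in 8.3.1 and 8.5.3, which already test the stop date, govern classification.

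Under these rules record A becomes 1 January to 10 April (31 + 28 + 31 + 10 = 100 days), B becomes 1 January to 31 March (31 + 28 + 31 = 90 days) and C becomes 1 to 6 May (6 days). D, E and F are unchanged.

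The cost is a few lines of SAP wording and minor programming, with no new data. The downside is that a few records with ambiguous dates stay prior rather than concomitant.

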8. STATISTICAL METHODS

8.1. General Principles of Data Analyses

The primary analysis for this study will be performed and summarized after all randomized participants have had an opportunity to complete their 6-month follow-up visit.

The Safety Analysis will be based on the Safety population. The primary analyses of the efficacy endpoints will be based on the ITT population. Additional sensitivity analyses for the primary and secondary efficacy endpoints will be performed to further assess the effects of the treatment (Section 8.4.2 and 8.4.4).

The statistical analyses will be reported using summary tables, figures and listings. Continuous variables will be summarized with means, standard deviations, medians, minimums, maximums, 25th percentiles, 75th percentiles, and number of non-missing observations for each treatment group.

Categorical variables will be summarized by counts and by the percentage of participants in corresponding categories.

All inferential statistical analyses will be performed with a two-sided confidence level of 95% or a two-sided significance level of 0.05 unless otherwise noted.

All analyses and tabulations will be performed using SAS Version 9.4 or higher on a Server platform.

8.2. Participant Enrollment and Disposition

The reasons for participant enrolled but not randomized (including screen failures) will be summarized by the specific inclusion/exclusion not met for screen failures and any other reasons provided. Participant disposition will be summarized for all randomized participants. The summary including the number and percentage (based on total number of participants randomized) of participants in each of the following categories will be prepared:

- Available at each of the protocol-specified visits based on the ITT population
- Completing 6-month blinded assessment based on the ITT population
- Early Termination based on the ITT population
- Safety population, ITT, mITT, and PP populations

Major protocol deviations for participants not in the PP populations will be listed. Major protocol deviations will be summarized for the ITT population.

8.3. Demographics and Baseline Characteristics

The following outcomes will be summarized by the standard methods for continuous and categorical variables described in Section 8.1.

The demographics include the following parameters:

- Age at informed consent
- Sex
- Race
- Ethnicity

The baseline characteristics include the following:

- Baseline Average Daily Pain Score from the 7 days prior to the Day 0 Visit obtained from the BPI-DPN eDiary
- Vital signs: blood pressure, weight, BMI, heart rate, respiration rate, temperature
- Diabetes type
- 12-lead electrocardiogram (ECG): Normal, Abnormal Not Clinically Significant (NCS), Abnormal Clinically Significant (CS)

These parameters will be summarized by treatment group for the ITT and included in data listings. The demographic and selected baseline characteristics (diabetes type and specific medical history items of interest) will also be summarized for each level of the stratification variable.

8.3.1. Prior and Concomitant Medications

Prior medications are those medications taken within 30 days of the first injection of study drug. Concomitant medications are those medications taken after the initial dose of study drug. A medication with a missing start date and a stop date that is either missing or on or after the treatment start date will be considered as concomitant. All prior and concomitant medications will be assigned WHO drug names using the WHO Drug Dictionary (March 2018 version or later). Prior and concomitant medications will be summarized separately for each treatment group by preferred names. These summaries will present the number and percentage of participants using each medication.

[figure not shown]
8.3.2. Medical History

[figure not shown]
Abnormalities in participants' medical and surgical histories will be coded using the Medical Dictionary for Regulatory Activities (MedDRA). The number and percentage of participants with abnormalities in medical and surgical histories in each system organ class (SOC) and preferred term will be summarized by treatment group for the ITT population.

[figure not shown]
In addition, medical history of interest will be summarized separately. Particular medical histories of interest, based upon MedDRA SOC and preferred terms, will be determined by the CDRC in a blinded fashion prior to analyses.

8.4. Efficacy Endpoints Analyses

8.5. Safety Analyses

Safety analyses in this study will evaluate the safety profile of Engensis as compared with control. No formal statistical testing will be conducted for the safety analyses. The following sections summarize the descriptive analysis methods for these safety endpoints. All participants in the Safety population will be included in these analyses. Participants will be grouped by treatment administered. All summaries will be derived based on available data. No imputation will be performed for missing values.

8.5.1. Study Drug Exposure

Study drug exposure (number of injections, total volume and total milligrams administered per calf) will be summarized by treatment group by mg of Engensis for Day 0, Day 14, Day 90, Day 104, and overall using descriptive statistics for continuous variables.

8.5.2. Injection Site Reaction Assessments

The number and percentage of participants with an injection site AE will be summarized descriptively overall and by type (injection site reaction, ulceration, allergic reaction / hypersensitivity) by treatment group and study visit. The number and percentage of participants with a given type of injection site AE will be summarized by grade and treatment group for the pre- and post-injection assessments on Days 0, 14, 90, and 104; only participants who receive an injection at a given one of these visits will be counted in the post-injection assessment results for that visit. Participants without an injection site AE of a particular type will be assigned a grade of 0 for these summaries.

8.5.4. Cytokine Profile

The absolute values and the change from baseline value will be summarized using descriptive statistics for each treatment group.

8.5.5. Anti-Hepatocyte Growth Factor (HGF) Antibodies

The presence of anti-HGF antibodies will be summarized by its frequency and percentage for each treatment group.

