### 3. OBJECTIVES AND ENDPOINTS

Objectives	Endpoints
Primary	

 
To evaluate the efficacy of IM administration of Engensis on pain in Participants with painful DPN in the feet and lower legs as compared to Placebo
 
	
 
Change in the means of the Average Daily Pain Scores (ADPSs) from the Brief Pain Inventory for Diabetic Peripheral Neuropathy (BPI-DPN) from the 7 days prior to the Day 0 Visit to the 7 days prior to the Day 180 Visit for Engensis compared to Placebo in the intent-to-treat (ITT) population
 

Secondary Efficacy	

 
To evaluate the efficacy of IM administration of Engensis on the worst pain in Participants with painful DPN in the feet and lower legs as compared to Placebo
 
	
 
Change in the means of the Worst Pain scores from the BPI-DPN from the 7 days prior to the Day 0 Visit to the 7 days prior to the Day 180 Visit for Engensis compared to Placebo
 

 
To evaluate the efficacy of IM administration of Engensis on reducing pain in Participants with painful DPN in the feet and lower legs as compared to Placebo
 
	
 
Proportion of Responders (<math>\geq 50\%</math> reduction in the means of ADPSs from the BPI-DPN) from the 7 days prior to the Day 0 Visit to the 7 days prior to the Day 180 Visit for Engensis compared to Placebo
 

Secondary Safety	

 
To evaluate the safety of IM administration of Engensis in Participants with painful DPN in the feet and lower legs as compared to Placebo
 
	
 
Incidence of treatment-emergent adverse events (TEAEs) and treatment-emergent serious adverse events (TESAEs) for Engensis compared to Placebo
 
Incidence of injection site reactions for Engensis compared to Placebo
 
Incidence of clinically significant laboratory values for Engensis compared to Placebo
 

 
To evaluate the possibility of cellular and/or humoral responses to Engensis compared to Placebo in Participants with painful DPN in the feet and lower legs
 
	
 
Change from Baseline in the cytokine profile through post-dose to Day 104 for Engensis compared to Placebo
 

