#### 4.1.1. First Treatment Cycle

Prior to the First Treatment Cycle, in addition to vital signs, physical exam, drug tests, and medical history, the full BPI-DPN, BST, SF-36, and EQ-5D will be administered, and blood will be collected to obtain baseline values of selected cytokines, anti-HGF antibodies, and for safety laboratory assessments (see SoA, Section 1.3). A urine pregnancy test will also be conducted on women of childbearing potential.

Participants will receive Engensis or Placebo by IM injections in the gastrocnemius muscle on both legs on Day 0 and Day 14 as shown in Table 2.

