#### **8.6. Immunogenicity Assessments**

Pre-dose and post-dose (after 2 hours  $\pm$  1 hour post last injection) blood samples will be collected on Days 0 and 14, post-dose on Day 90, and pre-dose and post-dose samples will be collected on Day 104 for measurement of levels of TNF- $\alpha$ , IL-1 $\beta$ , IFN- $\gamma$ , IL-6, IL-4, IL-10, and IL-12p70.

A blood sample will be collected pre-dose on Days 0 and 90, and on Days 60, 150, and 180 for detection of anti-HGF antibodies.

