2. OBJECTIVES AND ENDPOINTS

Objectives			Endpoints
Pr	imary		
•	To evaluate the efficacy of IM administration of Engensis on pain in participants with painful DPN in the feet and lower legs, as compared to Placebo	•	Change in the means of the Average Daily Pain Scores (ADPSs) from the Brief Pain Inventory for Diabetic Peripheral Neuropathy (BPI-DPN) from the 7 days prior to the Day 0 Visit to the 7 days prior to the Day 180 Visit for Engensis compared to Placebo in the intent-to-treat (ITT) population
Secondary Efficacy			
•	To evaluate the efficacy of IM administration of Engensis on the worst pain in Participants with painful DPN in the feet and lower legs as compared to Placebo	•	Change in the means of the Worst Pain Scores from the BPI-DPN from the 7 days prior to the Day 0 Visit to the 7 days prior to the Day 180 Visit for Engensis compared to Placebo
•	To evaluate the efficacy of IM administration of Engensis on reducing pain in Participants with painful DPN in the feet and lower legs as compared to Placebo	•	Proportion of Responders (≥ 50% reduction in the means of ADPSs from the BPI-DPN) from the 7 days prior to the Day 0 Visit to the 7 days prior to the Day 180 Visit for Engensis compared to Placebo

	Objectives		Endpoints
Sec	condary Safety		
•	To evaluate the safety of IM administration of Engensis in Participants with painful DPN in the feet and lower legs as compared to Placebo		Incidence of treatment-emergent adverse events (TEAEs) and treatment-emergent serious adverse events (TESAEs) for Engensis compared to Placebo Incidence of injection site reactions for Engensis compared to Placebo Incidence of clinically significant laboratory values for Engensis compared to Placebo
•	To evaluate the possibility of cellular and/or humoral responses to Engensis compared to Placebo in Participants with painful DPN in the feet and lower legs		Change from Baseline in the cytokine profile through post-dose on Day 104 for Engensis compared to Placebo Presence of anti-hepatocyte growth factor (HGF) antibodies following Engensis administration compared to Placebo
Ex	ploratory Efficacy		
•	To evaluate the efficacy of IM administration of Engensis on Quality of Life and Patient Reported Outcomes in Participants with painful DPN in the feet and lower legs as compared to Placebo	•	Patient Global Impression of Change (PGIC) on Day 90 and on Day 180 for Engensis compared to Placebo

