4.4. Safety Outcomes

Safety analyses in this study will evaluate the safety profile of Engensis as compared with Placebo. No formal statistical testing will be conducted for the safety analyses. All participants in the safety subset will be included in these analyses. Participants will be grouped by treatment received. All summaries will be derived based on available data. No imputation will be performed for missing values. All safety analyses will be made on the Safety Population.

- Change from Baseline (Day 0) in the cytokine profile through post-dose to Day 104 for Engensis compared to Placebo
- Presence of anti-hepatocyte growth factor (HGF) antibodies following Engensis administration compared to Placebo
 - HGF antibodies will be collected on Day 0, 60, 90, 150 and 180, and the presence will be summarized according to each time point.
- Adverse events
- · Injection site reaction assessment
- Vital signs
 - Blood pressure
 - Weight
 - Heart rate
 - Respiration rate
 - Oxygen saturation
 - Temperature
- HbA1c
- Laboratory values (Serum chemistry and hematology)
- Retinal fundoscopy

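### Anti-HGF antibody presence is tabulated visit by visit without reference to each participant's Day 0 result, so the tables cannot say how many participants became positive

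*SAP*

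**What the plan says.** The objective behind this endpoint, in Protocol section 3 and again in SAP section 2, is "To evaluate the possibility of cellular and/or humoral responses to Engensis compared to Placebo". The antibody endpoint attached to it is "Presence of anti-hepatocyte growth factor (HGF) antibodies following Engensis administration compared to Placebo".

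Protocol 8.6 sets the sampling: "A blood sample will be collected pre-dose on Days 0 and 90, and on Days 60, 150, and 180 for detection of anti-HGF antibodies". Protocol 4.1.1 makes clear why the Day 0 sample is drawn: "blood will be collected to obtain baseline values of selected cytokines, anti-HGF antibodies, and for safety laboratory assessments".

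Two places in the SAP describe the analysis. Section 4.4 reads "HGF antibodies will be collected on Day 0, 60, 90, 150 and 180, and the presence will be summarized according to each time point". Section 8.5.5 reads "The presence of anti-HGF antibodies will be summarized by its frequency and percentage for each treatment group", and does not repeat the by-time-point wording. For the cytokine half of the same objective, SAP 8.5.4 reads "The absolute values and the change from baseline value will be summarized using descriptive statistics for each treatment group".

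**The concern.** A response is a change within a person: negative before dosing and positive afterwards, or a rise in an antibody already present. The planned tables are marginal. Each column is the percentage positive on one day, and nothing carries a participant from one column to the next. Three things follow.

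- A participant who is positive on Day 0 and stays positive is counted again on Days 60, 90, 150 and 180, and looks the same as a new positive.
- A participant who becomes positive once and then reverts, or leaves the study, appears in one column only. The proportion who ever became positive is not reported.
- Missing antibody results are not imputed (SAP 7.6.2), so the denominator can differ between visits and a change in percentage may reflect who was sampled.

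This is a listed secondary safety endpoint for a plasmid given in two treatment cycles. As planned, the report could not state how many Engensis participants developed antibodies to the expressed protein.

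**Working it through.** The plan gives no anti-HGF prevalence, conversion rate or precision, so there is no figure to reproduce. The check compares the relevant sections and then works three illustrations. The only input from the documents is the group size: a target of 152 randomized 1:1 (SAP section 5), so 152 / 2 = 76 per arm. All antibody rates below are assumed.

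**What the sections do and do not provide**

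- SAP 7.1 defines a baseline for every variable, and Protocol 4.1.1 collects one for anti-HGF. SAP 8.5.5 does not use it.
- Other safety data are set against the pre-dose state: change from baseline for cytokines (8.5.4) and vital signs (8.5.6), a treatment-emergent definition for adverse events (8.5.3), and shift tables for laboratory values (8.5.7). The panels named for the shift tables are hematology and serum chemistry, not anti-HGF.
- No criterion in Protocol 5.1 or 5.2 excludes a Day 0 positive.
- Neither document plans a conversion rate, a Day 0 by post-dose shift or a titre comparison for anti-HGF.

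**Illustration 1: nobody positive on Day 0.** Four of 76 Engensis participants are each positive at a different one of the four post-dose visits, with all 76 sampled every time.

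- Each visit column: 1 / 76 = 1.3%.
- Ever positive after dosing: 4 / 76 = 5.3%.

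No planned table shows the 5.3%. This loss does not depend on pre-existing antibodies.

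**Illustration 2: the same margins from different histories.** Suppose 4 of 76 are positive on Day 0 and 4 of 76 on Day 180, so both columns show 4 / 76 = 5.3%. The Day 0 negatives number 76 - 4 = 72.

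- If the same four persist, conversion among Day 0 negatives is 0 / 72 = 0%.
- If the first four have turned negative and four others have converted, it is 4 / 72 = 5.6%.

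The by-visit table is identical in the two cases.

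**Illustration 3: how far pre-existing positivity dilutes the comparison.** Let b be the Day 0 prevalence in both arms and i the induction rate among Day 0 negatives on Engensis, with no induction on Placebo and all positivity persisting.

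- Presence on Engensis = b + (1 - b)i; presence on Placebo = b.
- Difference = (1 - b)i.
- Pre-existing share of Engensis positives = b / [b + (1 - b)i].

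| i | b | Engensis | Placebo | Difference (points) | Pre-existing share |
|---|---|---|---|---|---|
| 5% | 0% | 5.0% | 0% | 5.0 | 0% |
| 5% | 5% | 9.8% | 5% | 4.8 | 51% |
| 5% | 10% | 14.5% | 10% | 4.5 | 69% |
| 5% | 20% | 24.0% | 20% | 4.0 | 83% |
| 10% | 0% | 10.0% | 0% | 10.0 | 0% |
| 10% | 5% | 14.5% | 5% | 9.5 | 34% |
| 10% | 10% | 19.0% | 10% | 9.0 | 53% |
| 10% | 20% | 28.0% | 20% | 8.0 | 71% |

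The between-arm difference shrinks only by the factor (1 - b). The composition of the positives changes much more. Conversion among Day 0 negatives stays at i versus 0 whatever b is.

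**The case against.** A reader might infer that the endpoint counts any positive result after dosing, so that pre-existing antibodies are reported as a response and induced antibodies are hidden. The documents do not support that. No pooled post-dose count is planned: SAP 4.4 summarizes each time point separately. Day 0 is one of those time points, so pre-existing positivity is shown by arm beside the later columns. The comparison is with a 1:1 randomized Placebo arm, in which pre-existing positives are expected at the same rate, and the dilution is mild: from 5.0 to 4.8, 4.5 or 4.0 points on the assumed rates. Day 0 prevalence may also be low, because Protocol 5.2 (criterion 33) excludes people who took part in an earlier Engensis study.

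Further points on that side are fair. SAP 8.5.5 implements the endpoint as it is worded, which is presence. The contrast with cytokines proves little by itself, since change from baseline is the named endpoint there. Safety analyses carry no formal test, so an argument from standard errors or power would bear on no planned decision. All five samples are collected anyway, so a cross-tabulation could be added at reporting without loss of data.

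The by-visit margins still cannot distinguish new from persistent positives or give an ever-converted proportion, with or without pre-existing antibodies. A definition chosen once results are known is also weaker than one fixed beforehand.

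**Conclusion.** The point holds in a limited form. Per-visit presence by arm is planned, and it answers how common anti-HGF antibodies are on a given day. It does not answer how many participants developed them, which is the question in the objective. Induced antibodies are diluted and cannot be separated from pre-existing ones; they are not hidden.

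The size cannot be fixed from the documents. With no Day 0 positives there is no mixing, and what is missing is the ever-converted proportion (5.3% against 1.3% per visit in the constructed example). With an assumed Day 0 prevalence of 5% to 20% and 10% induction, 34% to 71% of Engensis positives at a post-dose visit would be pre-existing, while the arm difference would be 9.5 to 8.0 points instead of 10. These figures assume persistent positivity, no induction on Placebo and equal Day 0 prevalence in the arms.

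The consequence is for the interpretation of a descriptive safety endpoint. Alpha, power, sample size and the primary conclusion are not affected.

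**What to change.** In SAP 4.4 and 8.5.5:

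1. Add treatment-emergent anti-HGF positivity, defined as Day 0 negative with any positive sample on Days 60 to 180. Report it by arm, with Day 0 negatives who have at least one post-dose sample as the denominator.
2. Add a Day 0 by post-dose shift table for each arm.
3. List Day 0 positives separately, with the rise in titre if the assay gives a titre.
4. Keep the by-visit presence table, so that the endpoint wording in the protocol still holds, and carry the time-point wording of 4.4 into 8.5.5.

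The cost is SAP wording and a small amount of extra output from samples already scheduled. There is one drawback. Pooling four post-dose samples accumulates assay false positives: at an assumed 1% per sample, independent across samples, 1 - 0.99^4 = 3.9% of Day 0 negatives in each arm would be classed as emergent. The rate should therefore always be shown beside Placebo and read with the by-visit table.
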